### **Beck Depression Inventory (BDI-II)**

BDI-II is the 1996 revision of BDI. It is a multiple-choice inventory including 21 items and it takes ~ 10 minutes to complete.

Beck Depression Inventory will be assessed to distinguish depression and cognitive impairment. The maximum total score is 63 and scores 0-13 indicates minimal depression, 14-19 indicates mild depression, 20-28 indicates moderate depression and 29-63 indicates severe depression. Beck Depression Inventory will be also performed to distinguish depression and cognitive impairment.

### **6.4.2 Magnetic Resonance Imaging (MRI) Assessments**

MRI scans will be obtained at baseline and at months 6, 12, 18 and 24 by using 1.5T MRI for measuring gray matter atrophy and thalamic atrophy.

A standard scanning protocol will be used for MRI in all centers.

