#### **2.3.2 Secondary endpoints:**

-To measure the difference in serum levels of 24S-hydroxycholesterol (24OHC) , osteopontin and matrix metalloproteinases (and also MMPI's) between baseline and after fingolimod treatment at month 12 and month 24.

-To evaluate the effect of fingolimod on cognitive performance in highly active relapsing remitting multiple sclerosis patients comparing baseline, month 12 and month 24, as assessed by PASAT and Stroop test.

-To evaluate the effect of fingolimod on brain gray matter atrophy and thalamic atrophy by comparing MRI data between baseline and month 24.

-To evaluate the correlation between effect of fingolimod on cognitive performances and brain atrophy (gray matter atrophy and thalamic atrophy) by comparing baseline and month 24.

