**Table 6-1 Assessment schedule**

Visit	Screening Period	1(Baseline) 	2	3	4	5	6
Month	-1 to 0	0	3	6	12	18	24
Obtain informed consent 	X						
Background / Demography	X						
Inclusion / exclusion criteria	X						
Medical history	X						
MS history / MS treatment	X						
Concomitant medication	X		X	X	X	X	X
Physical examination	X		X	X	X	X	X
Vital findings	X	X	X	X	X	X	X
Hematology	X		X	X	X	X	X
Serology	X						
Blood biochemistry	X		X	X	X	X	X
ECG	X	X					
Optical Coherence Tomography (OCT)	X		X				
Pregnancy test	X						
EDSS	X		X	X	X	X	X
6-hour first dose monitoring		X					
Beck Depression Inventory (BDI-II)		X		X	X		X
PASAT		X		X	X		X
Stroop test		X		X	X		X
BICAMS Battery		X		X	X		X
MRI		X		X	X	X	X
Collecting serum samples for biomarkers		X		X	X		X
Advers events / SAE	X	X	X	X	X	X	X

 All assessments must be performed after obtaining informed consents.

 At visit 1, all assessments must be performed before initiating the study drug.

Patients should be seen for all visits on the designated day with an allowed “visit window” of “±7” days at visit 2 and “±14” days at visit 3, 4, 5 or as close to it as possible, or as shortly after it as possible, or as shortly before it as possible and “±30” days for the last visit

At a minimum, patients will be contacted for safety evaluations during the 30 days following the last study visit or following the last administration of study treatment if there are post-treatment follow-up visits (whichever is later), including a final contact at the 30-day point. Documentation of attempts to contact the patient should be recorded in the source documentation.

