#### **9.4.3.1 Data analysis**

##### **General Approach**

All Statistical analyses will be performed with MedCalc Statistical Software version 13.1.2 (MedCalc Software bvba, Ostend, Belgium; <http://www.medcalc.org>; 2014) at the 5% significance level using 2-sided tests or 2-sided Confidence Intervals.

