##### **Secondary Objectives:**

Secondary objectives of the study will be evaluated by the statistical methods which are stated below:

- The effect of fingolimod on biomarkers (24OHC, Osteopontin and Metalloproteinase) at months 6, 12, 24 will be evaluated by comparing the levels of biomarkers. The evaluation among time points will be made by using Repeated Measures ANOVA.
- The effect of fingolimod on brain gray matter atrophy and thalamic atrophy will be evaluated by comparing MRI parameters at baseline, 6th, 12th, 24th months.

The comparison among time points will be made by Repeated Measures ANOVA. (if variables are non-normally distributed Friedman Test).

- Investigation the effect of fingolimod on cognitive performance in highly active relapsing remitting multiple sclerosis patients comparing baseline, 12th and 24th month, as assessed by PASAT and Stroop test will be made by Repeated Measures ANOVA. (if variables are non-normally distributed Friedman Test).
- Correlation between cognitive performance and MRI data will be calculated by using Pearson Correlation Coefficient (or Spearman Correlation Coefficient) between PASAT, STROOP and BICAMS tests scores and MRI parameters.

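### The Month 18 MRI is scheduled to measure atrophy but has no assigned comparison in the atrophy analysis or endpoint

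*Combined protocol and SAP*

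**What the plan says.** Three places in the combined protocol and SAP give the imaging schedule. Section 6.4.2 says that "MRI scans will be obtained at baseline and at months 6, 12, 18 and 24", and gives measurement of gray matter and thalamic atrophy as the purpose. Section 3.1 repeats this, and Table 6-1 marks MRI at the visits for Months 0, 6, 12, 18 and 24.

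The analysis text uses fewer scans. Under Secondary Objectives in 9.4.3.2, atrophy is evaluated by "comparing MRI parameters at baseline, 6 th , 12 th , 24 th months", and "The comparison among time points will be made by Repeated Measures ANOVA", with Friedman's test if the data are not normally distributed. Section 2.3.2 is narrower still. Its endpoint evaluates "brain gray matter atrophy and thalamic atrophy by comparing MRI data between baseline and month 24".

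So five scans are scheduled, four enter the planned comparison, and two define the endpoint. No section gives the Month 18 scan an inferential role or explains why it is left out.

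**The concern.** A research scan scheduled in every patient for a stated efficacy purpose should have a stated place in the analysis. Month 18 has none. Table 6-1 schedules no cognitive test or biomarker sample at that visit, so the scan cannot serve a same-visit correlation with cognition either. The atrophy analysis is its natural home.

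Two things are at stake, both modest. First, the study is open-label, and sections 3.4 and 9.7 allow for possible yearly interim analyses. If the use of Month 18 is not fixed in advance, it can be decided after results are seen. Second, a patient lost between Months 18 and 24 has Month 18 as the last observation, and the plan gives no missing-data rule for the efficacy comparisons. Section 9.4.3.1 only says how missing values are treated in percentages.

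**Working it through.** **Inputs from the documents.** Scan months 0, 6, 12, 18, 24 (3.1, 6.4.2, Table 6-1); analysis months 0, 6, 12, 24 (9.4.3.2); endpoint months 0 and 24 (2.3.2); testing "at the 5% significance level using 2-sided tests or 2-sided Confidence Intervals" (9.4.3.1); minimum 73 patients, 80 enrolled, 10% loss expected (9.6).

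**Not in the documents.** There is no variance, correlation, power or precision target for MRI. The 73 and 80 rest on the SDMT, so there is no MRI figure to reproduce. The variance and correlation values below are assumptions, shown as ranges.

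**1. The plan's endpoint and method, complete data.** In repeated measures ANOVA with error variance σ², the Month 24 minus baseline contrast has variance 2σ²/n, with or without Month 18. The gain is 0%. The only change is in error degrees of freedom. At n = 73 they go from 72 × 3 = 216 to 72 × 4 = 288, the critical t goes from 1.9710 to 1.9682, and the confidence interval narrows by about 0.14%.

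**2. Same contrast, mixed model with visit as a category, with dropout.** Take 73 completers and 7 patients lost (80 − 73, or 8.75%). The reduction in contrast variance from including Month 18 is:

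| Assumed covariance | All 7 miss Month 24 only | 7 losses spread over follow-up (last scan: 1 at baseline, 2 each at Months 6, 12, 18) |
|---|---|---|
| Constant correlation 0.9 | 0.35% | 0.11% |
| Random intercept and slope (variances 0.9 for intercept, 0.1 for change over 24 months, 0.1 residual) | 0.86% | 0.26% |
| AR(1), 0.98 per month | 2.01% | 0.61% |

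The range is about 0.1% to 2%.

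**3. A linear slope (not in the plan).** With independent residuals, slope information is proportional to Sxx = Σ(t − t̄)².

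- Months 0, 6, 12, 24: t̄ = 10.5; Sxx = 110.25 + 20.25 + 2.25 + 182.25 = 315.
- Months 0, 6, 12, 18, 24: t̄ = 12; Sxx = 144 + 36 + 0 + 36 + 144 = 360.
- Variance ratio 315/360 = 0.875, so variance falls 12.5% and the standard error falls 1 − √0.875 = 6.5%.

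This is the ceiling. If patients differ in their true slopes, the variance is proportional to 1/Sxx + (r/24)², where r is the slope SD over 24 months divided by the residual SD. The reduction is 8.1% at r = 1, 3.9% at r = 2 and 2.1% at r = 3. With AR(1) residuals and a monthly correlation of 0.90 or more, it is about 0.6% or less.

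**4. Adding Month 18 to a complete-case ANOVA.** The plan does not say how incomplete patients are handled. If only patients with every scan are kept, a further fraction m lost for want of Month 18 multiplies the contrast variance by 1/(1 − m). At m = 5% this is 1/0.95 = 1.053, a rise of about 5%. At m = 12.5% even the best-case slope gain disappears: 0.875/0.875 = 1.

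**The case against.** The defence of the plan is strong on precision. The endpoint is a two-point change, and for that change the planned method loses nothing with complete data by ignoring Month 18. The dropout argument is real for the individual patient but touches few: 10% loss is expected over 24 months, and only part of it can fall after Month 18. This stands, and it limits the size of the point.

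It can also be said that the scan is not wholly unused. The descriptive statistics in 9.4.3.1 are not restricted by visit, nothing in 9.4.2 limits which scans are measured, and section 5.4.9 lists MRI findings among the results that may bear on stopping study drug. This also stands. What is missing is an assigned comparison; nothing says that the scan will go unmeasured or unreported.

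Finally, a model with straight-line time would change the estimand, and a Month 24 change read from a fitted line would be biased if atrophy is not linear. This is a sound objection to making a slope the main analysis. It does not apply to a model with visit as a category, which keeps the Month 24 contrast as defined. None of these arguments explains why 2.3.2, 6.4.2 and 9.4.3.2 name different sets of visits.

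**Conclusion.** The inconsistency is established from the text: Month 18 MRI is scheduled for measuring atrophy and has no assigned comparison. It is minor. It concerns a secondary endpoint and does not touch the BICAMS primary endpoint or the sample size.

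A reader might infer that the plan throws away useful precision, since five scans carry 14% more slope information than four (360/315 = 1.143). The documents do not support that reading. The figure belongs to a linear slope that the plan does not define, and it needs independent residuals and no variation in slope between patients. A reader might also take the scan as obtained in everyone; it is scheduled for everyone, and withdrawn patients will lack it. Nor do the documents show whether the omission is an oversight. The analysis visits match the cognitive and biomarker schedule, which suggests a carry-over but does not prove one.

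The case for change is therefore consistency, pre-specification and retention of patients with a missed visit. Any precision gain is a small extra, and its size rests on the assumed covariances.

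**What to change.** In 9.4.3.2, replace the repeated measures ANOVA for MRI volumes with a mixed model for repeated measures that has visit as a categorical factor and uses all available scans at baseline and Months 6, 12, 18 and 24. Report the Month 24 minus baseline change from this model as the endpoint, which keeps 2.3.2 intact. An annual rate from a linear-time model may be given as supportive only. State how missing scans are handled, and whether the Friedman fallback is kept as a sensitivity analysis.

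Do not simply add Month 18 to a complete-case repeated measures ANOVA, because each patient missing that scan would be lost.

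The cost is a short text change. Because the analysis sits in the protocol, it needs a written amendment under section 11.1. Section 9.4.3.1 names one software package for all analyses, so someone must first confirm that it can fit this model, or the amendment must name one that can. No visit, scan or patient is added.

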#### MRI scanning protocol:

MR imaging studies will be performed using a 1.5 Tesla scanner with a dedicated head coil. Patients will be placed in supine position.

For volumetric measurements, 3D T1 FFE sequence will be obtained. Parameters will be as TE: 2.3 ms, TR: 5.1ms, Flip angle: 8°, 1 mm slice thickness, TFE factor: 232, TFE shots: 46

MRI scans will be sent to the Kocaeli University Faculty of Medicine which is the center of the study coordinator investigator for atrophy analysis.

### **6.4.3 Biomarkers**

Serum samples will be collected at baseline and at months 6, 12 and 24 from each participant after evaluation for inclusion and exclusion criteria for measurement of 24 hydroxy cholesterol, osteopontin and matrix metalloproteinases (including MMP1's).

### **6.4.4 Expanded Disability Status Scale (EDSS)**

EDSS is a scale for assessing neurologic impairment in MS (Kurtzke 1983) including (1) a series of scores in each of eight functional systems, and (2) the EDSS steps (ranging from 0 (normal) to 10 (death due to MS)). The functional systems are Visual, Brain Stem, Pyramidal, Cerebellar, Sensory, Bowel & Bladder, Cerebral and Other functions. It is recommended that fatigue is not included in the Cerebral score of the EDSS.

EDSS will be assessed by the investigator at each site, who has successfully completed his/her certification requirements. EDSS assessments are scheduled at screening and at month 3, 6, 12, 18 and 24.

## **6.5 Safety**

### **6.5.1 Laboratory evaluations**

#### **6.5.1.1 Hematology**

Hematology parameters will be collected at screening and other visits as shown in the assessment schedule and will include: WBC count, absolute lymphocytes, platelet, absolute neutrophil count, and hemoglobin.

#### **6.5.1.2 Clinical chemistry**

Blood samples will be collected at screening and at each scheduled visit to verify a patient's eligibility and will include but not limited to the following parameters: AST, ALT, BUN, Creatinine, Total Cholesterol, Triglycerides, LDL-K, HDL-K, TSH, ST4, Glucose, HbA1c

### **6.5.2 Electrocardiogram (ECG)**

A standard 12 lead ECG will be performed at screening, right before the intake of the first dose of the study drug and after 6 hours of the intake of the study drug. Interpretation of the tracing must be made by a qualified physician and documented on the ECG section of the CRF. Each ECG tracing should be labeled with the study and subject number, date, and kept in the source documents at the study site. Clinically significant abnormalities should also be recorded on the Medical History/Adverse event CRF page. Clinically significant findings must be discussed with the Novartis Medical Monitor prior to enrolling the patient in the study.

### **6.5.3 Optical Coherence Tomography (OCT)**

An optical coherence tomography for the eyes will be performed in screening and in Visit 2. The tracing of the OCT must be made by a qualified physician and documented on the OCT section of the CRF. Each OCT tracing should be labeled with the study and subject number, date, and kept in the source documents at the study site. Clinically significant abnormalities should also be recorded on the Medical History/Adverse event CRF page. Clinically significant findings must be discussed with the Novartis Medical Monitor prior to enrolling the patient in the study.

### **6.5.4 Pregnancy and assessments of fertility**

All pre-menopausal women who are not surgically sterile will have a urine pregnancy test. A positive urine pregnancy test requires immediate interruption of study drug until serum  $\beta$ -hCG is performed and found to be negative. If positive, the patient must be discontinued from the trial.

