## 6 Visit schedule and assessments

Table 6-1 lists all of the assessments and indicates with an “x” when the visits are performed.

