## **7 Safety monitoring**

### **7.1 Adverse events**

An adverse event (AE) is any untoward medical occurrence (i.e., any unfavorable and unintended sign [including abnormal laboratory findings], symptom or disease) in a subject or clinical investigation subject *after providing written informed consent* for participation in the study. Therefore, an AE may or may not be temporally or causally associated with the use of a medicinal (investigational) product.

The occurrence of adverse events should be sought by non-directive questioning of the patient at each visit during the study. Adverse events also may be detected when they are volunteered by the patient during or between visits or through physical examination, laboratory test, or other assessments.

Abnormal laboratory values or test results constitute adverse events only if they fulfill at least one of the following criteria:

- they induce clinical signs or symptoms,
- they are considered clinically significant,
- they require therapy.

Clinically significant abnormal laboratory values or test results should be identified through a review of values outside of normal ranges/clinically notable ranges, significant changes from baseline or the previous visit, or values which are considered to be non-typical in patient with underlying disease. Investigators have the responsibility for managing the safety of individual patient and identifying adverse events. Alert ranges for labs and other test abnormalities are included in Appendix 1.

Adverse events should be recorded in the Adverse Events CRF under the signs, symptoms or diagnosis associated with them accompanied by the following information.

- the severity grade
  - mild: usually transient in nature and generally not interfering with normal activities

- moderate: sufficiently discomforting to interfere with normal activities
- severe: prevents normal activities
- its relationship to the (*select what is applicable*) study treatment (no/yes), or investigational treatment (no/yes), or the other study treatment(non-investigational) (no/yes), or both or indistinguishable,
- its duration (start and end dates) or if the event is ongoing an outcome of not recovered/not resolved should be reported.
- whether it constitutes a serious adverse event (SAE)
- action taken regarding study treatment
- whether other medication or therapies have been taken (concomitant medication/non-drug therapy)

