### **7.3 Pregnancy reporting**

To ensure patient safety, each pregnancy occurring while the patient is on study treatment must be reported to Novartis within 24 hours of learning of its occurrence. The pregnancy should be followed up to determine outcome, including spontaneous or voluntary termination, details of the birth, and the presence or absence of any birth defects, congenital abnormalities, or maternal and/or newborn complications.

Pregnancy should be recorded on a Clinical Trial Pregnancy Form and reported by the investigator to the local Novartis Drug Safety and Epidemiology Department. Pregnancy follow-up should be recorded on the same form and should include an assessment of the possible relationship to the study treatment.

Any SAE experienced during pregnancy must be reported on the SAE Report Form.

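### Section 6.5.4 stops study drug on a positive urine pregnancy test, but Table 6-1 schedules that test only at screening; add it before the first dose and at Visits 2 to 6

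*Combined protocol and SAP*

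**What the plan says.** Section 6.5.4 provides that pre-menopausal women who are not surgically sterile have a urine pregnancy test, without naming a visit. It continues: "A positive urine pregnancy test requires immediate interruption of study drug". The interruption lasts until serum hCG is found negative; if serum hCG is positive, the patient is discontinued from the trial.

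Section 6 opens with "Table 6-1 lists all of the assessments". In that table the pregnancy-test row has a single mark, in the screening column (month -1 to 0). The cells for Visit 1 (baseline) and Visits 2 to 6 (months 3, 6, 12, 18 and 24) are empty.

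The two sections just before 6.5.4 do state their times. Section 6.5.2 has the ECG "performed at screening, right before the intake of the first dose of the study drug" and again 6 hours after it. Section 6.5.3 says "An optical coherence tomography for the eyes will be performed in screening and in Visit 2".

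Elsewhere, section 4.2 excludes pregnant women, section 5.4.9 lists pregnancy among the grounds for stopping drug, and section 7.3 requires that "each pregnancy occurring while the patient is on study treatment must be reported to Novartis within 24 hours".

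**The concern.** A drug can be interrupted only if the patient is already taking it, so the rule in section 6.5.4 is written for women on treatment. The schedule contains no test on treatment. The rule, the discontinuation that follows it and the 24-hour report in section 7.3 all act once a pregnancy is known. Nothing in the schedule is designed to find one.

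Two things are at stake. First, the pregnancy exclusion may rest on a test up to a month old when the first dose is given, whereas the ECG is repeated immediately before that dose. Second, treatment lasts 24 months and section 5.4.2 has drug dispensed every 3 months. A site that follows Table 6-1 to the letter could go on dispensing to a woman whose pregnancy has not been recognised. Recognised pregnancies are already handled; the gap is in detection.

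**Working it through.** The plan gives no figure to reproduce. The check sets the text against the table, followed by simple arithmetic on gaps.

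**1. Is the table read correctly?** The columns were checked against rows whose times also appear in the text.
- ECG row: marks at screening and Visit 1, agreeing with section 6.5.2.
- OCT row: marks at screening and Visit 2, agreeing with section 6.5.3.

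The columns line up, so the one pregnancy-test mark belongs to screening.

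**2. Does anything else schedule a test?**
- The Visit 1 footnote says "At visit 1, all assessments must be performed before initiating the study drug". It orders what is done at Visit 1; it does not add a test that the row leaves blank.
- The chemistry panel in section 6.5.1.2 does not name hCG. Its list is open-ended, so hCG is permitted but not required.
- Section 7.1 says "The occurrence of adverse events should be sought by non-directive questioning of the patient at each visit during the study", and Table 6-1 has a physical examination at Visits 2 to 6. Either may prompt a test, but neither is one.
- Sections 5.4.9 and 7.3 apply after a pregnancy is known and set no test.

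**3. Count.** Time points: screening + Visits 1 to 6 = 7. Pregnancy tests marked: 1 of 7. From Visit 1 onward: 0 of 6.

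**4. Longest span without a scheduled test, as planned.** Inputs: screening up to 1 month before baseline; 24 months of treatment; last visit ±30 days; 1 month taken as 30.44 days.
- Nominal: 1 + 24 = 25 months, of which 24 are on drug.
- Last visit at +30 days: 25 + 30/30.44 = 26.0 months.

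This is a span without a scheduled test, not without clinical contact.

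**5. Gaps with tests at Visits 1 to 6.** Windows from Table 6-1: Visit 2 ±7 days; Visits 3 to 5 ±14 days; last visit ±30 days.

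| Interval | Nominal (months) | At the window limits (months) |
|---|---|---|
| Visit 1 to 2 | 3 | 3 + 7/30.44 = 3.2 |
| Visit 2 to 3 | 3 | 3 + (7 + 14)/30.44 = 3.7 |
| Visit 3 to 4 | 6 | 6 + (14 + 14)/30.44 = 6.9 |
| Visit 4 to 5 | 6 | 6 + (14 + 14)/30.44 = 6.9 |
| Visit 5 to 6 | 6 | 6 + (14 + 30)/30.44 = 7.4 |

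The longest nominal gap falls from 25 months to 6. The time from the last scheduled test to the first dose falls from up to 1 month to the same day.

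**6. Added tests.** Six per eligible woman. The number of eligible women is not given; if all 80 planned patients were eligible and completed every visit, 6 × 80 = 480.

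**The case against.** The strongest reply is that the two places do not contradict each other. Section 6.5.4 speaks of one urine test, which fits one mark, and the interruption rule can be read as a contingency for any positive result, including one from an unscheduled test. That reading is possible and the rule is not void. But it leaves detection on treatment to chance, which is the point at issue.

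A second reply is that testing or contraception guidance may sit elsewhere. Section 5.4.9 refers to Appendices 7 and 8, and section 5.4.5 to guidelines in an appendix. However, the table of contents lists only the appendix on the McDonald criteria, and no supplied text schedules a repeat test. Nothing is inferred here from consent pages, which were not available.

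Third, Table 6-1 is not fully exhaustive: section 5.4.4 has concomitant medication reconfirmed before the first dose, yet the table has no Visit 1 mark for it. This weakens an argument from an empty cell alone, but it does not show that a pregnancy test is planned.

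Three limits on the figures and the remedy do stand:
- Table 6-1 tolerates visits outside the windows where necessary, so real gaps could exceed those calculated. The synopsis calls 80 a minimum, so 480 holds only for 80 patients.
- With dispensing every 3 months, tests at the existing visits leave supplies due around months 9, 15 and 21 without a test. Testing at each dispensing would be tighter.
- The Visit 6 test comes at the end of treatment, so it does little for the interruption rule, though it helps find pregnancies that section 7.3 requires to be reported.

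**Conclusion.** The concern holds. The protocol has a stopping rule for women on treatment and no scheduled test on treatment to trigger it. Planned testing is confined to screening, leaving the first dose and all 24 months on drug without a scheduled test.

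The conclusion rests on the supplied text being complete on this point and on Table 6-1 being the operative schedule. It does not assume any pregnancy rate, and it does not claim that pregnancies would go unnoticed; questioning and examination may still prompt a test. The endpoint, the analysis and the sample size of 73 or 80 are unaffected. This is a patient-safety improvement that should be made because it is cheap and lets the protocol's own rule work.

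**What to change.** In Table 6-1, keep the screening test and mark the urine pregnancy test at Visit 1, before the first dose, and at Visits 2 to 6, for pre-menopausal women who are not surgically sterile. In section 6.5.4, add one sentence stating these times, as sections 6.5.2 and 6.5.3 do for ECG and OCT. If the sponsor wants closer cover, tests could also be tied to each 3-monthly dispensing; the change proposed here is the minimum that uses existing visits.

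The cost is six table marks, one sentence and six urine tests per eligible woman, with no added attendance. Under section 11.1 the change needs a written amendment with the usual approvals, and the paper case report forms described in section 8.2 may need a matching entry.
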